We propose to follow-up a sample of patients identified using the FARSITE database for the study that will be utilise data held by and run from Northern Care Alliance NHS Foundation Trust. We will invite GPs initially in Salford, but potentially extending into Greater Manchester to screen all adults (aged 18 years or over) registered with their practice using the FARSITE database (held by Northern Care Alliance NHS Foundation Trust in conjunction with NW e-Health). This process will identify patients with a positive SARS-CoV2 test since 20th July 2020 (when these data were routinely incorporated into GP records) and ensure study inclusion criteria are met and no exclusion criteria are present.

The study will be registered with ISRCTN and we will request Portfolio adoption by GM CRN.

\*Sponsor's representative: [name], Managing Director of Research & Innovation Norther Care Alliance NHS Foundation Trust, [name] [contact]; email: [contact]

We will conduct a wait-list RCT of an intervention which aims to help reduce fatigue using lymphatic self-massage alongside head and spinal mobility exercises and alternate warming and cooling of the upper spine. Together these intervention components will improve lymphatic drainage from the brain and spine to help alleviate the symptoms of fatigue. Progress over time will be determined by following up RCT participants at 3 and 6 months.

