#### Phase 2: Wait-list RCT Intervention Study

Those eligible will receive a PIS and CF explaining the Phase 2 RCT study either by email or by post. After 5 days, participants will be telephoned by a research practitioner based in Northern Care Alliance NHS Foundation Trust's Research delivery team.

100 participants providing informed consent will be allocated 1:1 into a two-arm wait-list randomised control trial (RCT) comparing lymphatic self-massage technique (the intervention) plus any usual care (UC) from their healthcare professionals vs. UC alone. This means any treatment received by participants will not be constrained. Those in the intervention group will receive instructions and equipment required via post as soon as they are randomised, with the UC wait-list group receiving their equipment 3 months later (after completion of their 3m follow-up), meaning all Phase 2 participants will be given access to the intervention. Both groups will be asked to complete follow-up measures at 3m and 6m.

Qualitative interviews will be conducted with 10 participants in the intervention arm at 3 months and a further 10 in each of the intervention arm and UC arms at 6 months to assess acceptability of the intervention, adherence to the intervention (over time for intervention group) and to explore potential barriers and drivers to its use.

#### **Detailed Plan of Investigation** 7

Research Activity		Done	Year and Month										Responsible		
			1 2 3 4 5 6 7 8 9 10 11 12 13 14 15								15				
		-	*	4	2 4	-	0	1	0 3	10	11 12	13		13	
re-work: On run up to	research becoming active											L			
PPIE	Consultation and patient input	1	L									L			LR/RP
FARSITE	Agree FARSITE search criteria with NW e-Health/CRN	-	L									L			LR/AH/CRN
	Run FARSITE search - Indicative numbers		L									L			CRN
Qualtrics Survey	Set up Phase 1 survey	-	L									L			SB/LR/AH/RP/MH
	Set up & test Phase 2 eligibility checks	-	L									L			SB/LR/AH
	Set up Phase 2 surveys at 3m and 6m		L									L			SB/LR/AH
Approvals	Sponsorship		L									L			AH/LR
	Ethical application (IRAS)		L									L			AH/LR
hase 1: Online Survey	Capacity & Capability checks: Salford & GM		H	-	-	-	-	-	_		_	-	-	-	AH/LR
Engagement with GP			4	-	_	-		-	-			-	-		SB LR / RA (CRN)
Survey launch	Eligible patients receive invite from their GP		5						-			-	-		SB
Survey launch	Implied consent by completing survey - 0m data		- 2					-		+		-	-		GP Staff (CRN)

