#### 7.1 Recruitment procedure

We will invite Salford GPs to screen their adult patients (aged 18 or over) whose notes indicate a previous positive SARS CoV-2 test for COVID-19 and reported in the last 12 weeks or more to participate in a prevalence study of fatigue-related symptoms. Screening will be facilitated using the FARSITE system (Hosted by Northern Care Alliance NHS Foundation Trust & NW e-Health). FARSITE when used as anonymised intelligence tool indicated 14,083 patients with a previous positive COVID-19 test. We plan to invite up to 32 GP practices whose number of patients is greater than 100 per practice to participate in order to generate the n=2,000 survey responses expected to recruit the 100 patients required into our Phase 2 study.

GPs will send a letter inviting patients who meet the study inclusion criteria to participate in a survey to look at Long COVID symptoms and their impact with some people being asked to participate in an intervention study to try to help reduce fatigue levels. This will be funded by [name] PI fund at the Northern Care Alliance NHS Foundation Trust.

Survey respondents in Phase 1 will be allocated a survey Participant ID number. Survey completion will predominantly be online, although paper copies will also be available for patients without internet / computer access. To facilitate this, a Research Practitioner (RA) based in the Research Delivery Team at Northern Care Alliance NHS Foundation Trust will assign a number manually on the recruitment log and enter it on the paper survey form that will be sent by post for completion along with a reply-paid envelope. Pseudonymised participant ID number will allow the RA will enter and link data to its respective participant but without compromising the confidentiality of clinical responses received. ID numbers will allow linkage to GP practice to monitor recruitment rates and to permit accrual data to be collected for the Local Care Research Network (LCRN).

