#### Phase 2: Long COVID Intervention Study

A Participant Information Sheet for Phase 2 and a consent form will then be displayed with an option to download a copy or request a copy by email or post. Participants will be provided with a contact number for the study co-ordinator in case participants have any questions before deciding if they wish to join the study. Since Phase 2 requires an additional and ongoing commitment, all potential participants will be asked to provide their name and a contact telephone number and/or email address.

Prior to joining the Phase 2 study, a Research Practitioner (costed at 40%) who is part of the Research Delivery Team based at No, will telephone patients complete the telephone-based consent form with them. Prospective participants will be asked if they have a nut allergy and if so, will be sent apricot kernel massage oil as an alternative to the almond oil which is routinely provided for participants.

Should recruitment fall below 80% of the number planned each month (20/25), we will recruit further GP practices and should we exhaust practices in Salford can extend recruitment into an adjacent area (Central Manchester CCG). Recruitment will be closely monitored at fortnightly research meetings and if across a 4-week period the recruitment falls below the trigger level stated, the additional recruitment areas will be added. Portfolio adoption has been sought for this study (for inclusion on Primary Care workstream). If successful, recruitment data will be submitted on a monthly basis to CRN.

Patients responding to the Phase 1 survey who meet Phase 2 entry criteria will receive an onscreen message telling them they are invited to participate. They will be able to access the Phase 2 PIS on screen to read and can complete their email, name and contact number if they would like to rake part.

They will then receive a copy of the Phase 2 PIS and Phase 2 consent form to the email address supplied. The research practitioner from NCA will telephone potential participants and will read through the consent form over the telephone and answer any queries participants might have.

Once patients have agreed to participate they will receive a copy of their telephone completed consent alongside their randomisation letter and/or intervention kit if selected to take part in the initial group.

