# 10 Statistical analyses and data handling

#### Analysis

This is a feasibility study, so we will not be carrying out formal hypothesis testing to determine if the intervention is effective. Data analysis will follow an Intention-To-Treat (ITT) protocol and will be used to inform power calculations for a definitive trial in addition to other published sources. Attrition and reasons for drop-out will be recorded where possible. We will assess rates of missing data (and which elements in particular) and proportions of dropouts at different trial stages. We will also assess whether any of the measures display floor and/ or ceiling effects.

We will calculate and present in a CONSORT (Eldridge et al, 2010) flow chart: the proportion of people with CFQ scores greater than or equal to 4, consenting to the study; those entering the randomised phase; the proportion completing 50% and 100% intervention (using patient reported compliance sheet); the proportion completing follow-up assessments at 3 and 6 months post-randomisation.

We will summarise, as appropriate (e.g. mean/ standard deviation; median/ inter-quartile range; proportion/ 95% confidence interval; data range) data for all potential outcome measures, overall and by group. Outcome data and changes (mean differences) in patient-reported measures between baseline (initial clinical assessment) and 3 and 6 month follow-up will be plotted with 95% confidence intervals by randomisation group on an intention to treat basis.

Adherence with the intervention will be measured and used to calculate an estimate of dose response. Where participants adhere to all 3 stages of the intervention fully – using the intervention as intended daily this will be deemed full intervention, with non-use of any stages of the intervention as a zero dose.

The SD of the (potential) Primary Outcome, along with the estimated attrition rate and the average number recruited per PCT/CCG (plus the range of this data) will be used to help inform the sample size calculation for the large-scale RCT.

The Primary feasibility outcomes will be recruitment and retention rates, and we will gain an estimate of likely effect sizes of the self-help intervention for a range of outcome measures and based on this determine the appropriate sample size for a larger trial to evaluate its effectiveness and cost-effectiveness versus standard treatments delivered within an NHS CFS/ME Service.

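### Section 10 plans a mean and range of recruitment per PCT/CCG as an input to the definitive trial, but the base plan recruits in one area only; the GP practice is the unit that varies

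*Protocol*

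**What the plan says.** The Analysis text of section 10 lists three inputs to the sample size of the later large-scale RCT: the SD of the potential primary outcome, the estimated attrition rate, and a site-level recruitment figure. On the third it says that "the average number recruited per PCT/CCG (plus the range of this data) will be used to help inform the sample size calculation".

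The recruitment plan is set out elsewhere in the protocol:

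- Section 6 (Phase 2: Wait-list RCT Intervention Study) fixes the size: "100 participants providing informed consent will be allocated 1:1 into a two-arm wait-list randomised control trial (RCT").
- Section 7.1 fixes the base area: "We will invite Salford GPs to screen their adult patients (aged 18 or over"). It also gives the number of practices: "We plan to invite up to 32 GP practices whose number of patients is greater than 100 per practice to participate".
- Section 7.1 says that "ID numbers will allow linkage to GP practice to monitor recruitment rates", so each participant can be traced to a practice.

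On extension beyond Salford the protocol has three statements of different breadth:

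- Section 4: "We will invite GPs initially in Salford, but potentially extending into Greater Manchester".
- Section 7.1 (Phase 2: Long COVID Intervention Study): further practices are sought if recruitment is below 80% of the monthly plan, and "should we exhaust practices in Salford can extend recruitment into an adjacent area (Central Manchester CCG").
- The same part of section 7.1, one sentence later: "if across a 4-week period the recruitment falls below the trigger level stated, the additional recruitment areas will be added".

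**The concern.** A mean and range across PCTs or CCGs can be informative only if several contribute and each is free to recruit what it can. Here one area is planned and the total is a fixed target. The planned summary is therefore either a single number or the target divided by a small number of areas opened at different times.

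Recruitment is one of the two primary feasibility outcomes in section 10, and a definitive trial needs to know how many sites to open and for how long. Between-site variation in recruitment is what answers that. Section 10 names a unit on which the base plan cannot show such variation, although the study will hold data on one that can.

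**Working it through.** **Inputs**

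- Phase 2 target 100 (section 6).
- Funnel in section 7.1: 4000 letters, 50% survey response, 10% with Long COVID symptoms, 50% uptake into Phase 2.
- Recruitment over 4 months; 25 planned per month; trigger at 80% (section 7.1).
- Up to 32 practices invited (section 7.1).
- Salford is counted here as one PCT/CCG. This is an assumption, in line with the protocol's treatment of it as one area next to a named CCG.

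**Step 1. Reproduce the plan's own figures.**
4000 × 0.50 = 2000 responses; 2000 × 0.10 = 200 screening positive; 200 × 0.50 = 100 randomised. Over time, 25 × 4 = 100, and the trigger is 0.80 × 25 = 20 per month. These agree with the protocol, so the plan on its own assumptions reaches 100 without leaving Salford.

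**Step 2. The planned summary when the target is met.**
Mean per area = total recruited / k, where k is the number of areas opened.

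| Areas (k) | Mean if 100 reached | Range |
|---|---|---|
| 1 (base plan) | 100/1 = 100 | none: one value |
| 2 (named adjacent CCG added) | 100/2 = 50 | two values |
| 3 (assumed) | 100/3 = 33.3 | three values |
| 4 (assumed) | 100/4 = 25 | four values |

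The rows for 3 and 4 are assumptions, because the protocol does not say how many areas a Greater Manchester extension would include.

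**Step 3. What a two-area range would show.**
For illustration, assume that Salford recruits at a constant rate for 4 months and the second area supplies the remainder up to 100.

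| Salford per month (assumed) | Salford total | Second area | Mean | Range |
|---|---|---|---|---|
| 19 | 19 × 4 = 76 | 24 | 50 | 24 to 76 |
| 15 | 15 × 4 = 60 | 40 | 50 | 40 to 60 |
| 10 | 10 × 4 = 40 | 60 | 50 | 40 to 60 |

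The mean is 50 in every row. Salford rates of 15 and 10 per month give the same mean and the same range, so the summary cannot tell them apart. The second area's count is simply what was left to fill.

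**Step 4. When the target is missed.**
If Salford recruits 19 per month, no area is added in time and recruitment closes at 4 months, the per-area figure is 19 × 4 = 76. That does carry information, but it is still one value with no between-site spread.

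**Step 5. The unit that is replicated.**
If all 32 invited practices joined, the plan implies per practice 4000/32 = 125 letters, 2000/32 = 62.5 survey responses and 100/32 = 3.1 randomised. If 16 joined (assumed), it would be 100/16 = 6.25 randomised. These averages are themselves the target divided by a planning number. The information lies in the spread across practices, and in using letters sent and months open as denominators.

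**The case against.** The strongest objection is that recruitment is well covered elsewhere. Section 7.1 monitors recruitment by practice and reviews it at fortnightly meetings against a monthly plan. Section 7.5 makes survey participation, recruitment and retention outcomes. Section 10 reports the proportions consenting, entering randomisation and completing follow-up. The per-PCT/CCG figure is one of three items that help inform a later calculation, alongside published sources. It plays no part in randomisation or in the outcome analyses here. All of this stands, and it limits the point to the site-level input.

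A reader might infer more than the documents support in four ways:

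- **That at most one further CCG could join.** Section 7.1 names one, but it also speaks of additional areas in the plural. Section 4 allows Greater Manchester, and the randomisation text provides for extra sites outside Salford. Three or more areas are possible.
- **That no range could ever exist.** This is strictly true only for one area. With two or more a range exists, but it says little.
- **That the figure is wholly set by the design.** This holds only if 100 is reached. A shortfall, or the time to target, would be a real finding.
- **That a Poisson interval around 100/32 would measure the gain from using practices.** It would not. A total recruited to a fixed target is not a free count, such an interval ignores variation between practices, and 32 is the maximum invited rather than the number taking part.

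It can also be said that reporting detail belongs in an SAP, which is not shown. That would answer a complaint about silence. Here the protocol itself names the unit and its use, and the planned design cannot usefully supply it.

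**Conclusion.** The point holds in a limited form. Under the base plan the mean per PCT/CCG is a single number, 100 at target, with no range. If a few areas are added and 100 is reached, the mean is 100 divided by the number of areas, and the range mainly reflects opening dates and the cap. Only a shortfall or the time to target would be informative.

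This rests on Salford counting as one PCT/CCG and on recruitment stopping at 100. A reader might conclude that the recruitment question goes unanswered. That is not supported, because the overall recruitment, consent and retention rates in section 10 do not depend on this figure. What is lost is a usable estimate of between-site variation, which a later trial needs when setting the number of sites and the recruitment period. The change is worth making because it is cheap and the practice-level link already exists.

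**What to change.** In the Analysis text of section 10, replace the mean and range per PCT/CCG with wording such as: *the number randomised per participating GP practice, per month open and per 100 invitation letters sent, with mean, SD and range across practices; practices in any area added after the start will be reported separately.* The SD and attrition inputs stay as they are.

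The practice-linked IDs supply the counts. The denominators require each practice's letter count and mailing date to be kept on the recruitment log. No extra participants or measures are needed.

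Sections 4 and 7.1 should also be reconciled on two matters: which areas recruitment may extend into, and whether the 4-week trigger alone is enough to add an area or Salford practices must first be exhausted.

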#### Follow-ups

Survey data collected in Phase 1 will be treated as baseline or 0-month data. Table 1 shows the schedule for subsequent study assessments. The CFQ, SF-12 and EQ5D-5D will be completed by the patient online or via a paper form returned to the research office. The 3m follow-up allows us to see any changes between those receiving the intervention and those not. The 6-month (6m) follow-up enables us to see if any benefits observed at 3m are maintained beyond the intervention period, and to compare this between the two groups.

	0m (baseline)	3m	6m
CFQ	Х	Х	Х
SF-12	Х	Х	Х
EQ-5D-5L	Х	Х	Х
Intervention diary		X (intervention group only)	X
Qualitative interview		X	X

Table 1: Assessments and timescales for the feasibility study

Proposed Primary outcome measures: These will be the logistical findings arising from the feasibility study (i.e. related to the conduct of the trial)

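### Section 10 ends by sizing the definitive trial on this study's own effect estimate, which is imprecise and is measured against a different comparator from the one that trial will use

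*Protocol*

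**What the plan says.** Three statements in section 10 (Analysis) bear on the size of the definitive trial.

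- Near the start, the data "will be used to inform power calculations for a definitive trial in addition to other published sources".
- Further on, the SD of a possible primary outcome and the attrition rate are listed as inputs, and with them "the average number recruited per PCT/CCG (plus the range of this data) will be used to help inform the sample size calculation".
- The section closes by saying that the study will estimate "likely effect sizes of the self-help intervention for a range of outcome measures and based on this determine the appropriate sample size". The trial to be sized in this way is one that takes NHS CFS/ME Service treatments as its comparator and looks at both effect and cost.

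The contrast that this study can estimate is set out elsewhere. Section 6 (Phase 2) describes a 1:1 trial of 100 participants "comparing lymphatic self-massage technique (the intervention) plus any usual care (UC) from their healthcare professionals vs. UC alone". The Follow-ups text in section 7.1 adds: "The 3m follow-up allows us to see any changes between those receiving the intervention and those not". After 3 months the wait-list arm also receives the intervention, so 3 months is the only time at which treated and untreated groups are compared. The protocol names no minimum important difference or margin.

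**The concern.** The closing sentence gives this study's observed effect the role of target difference for the next trial. Two things make it unsuited to that role.

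First, with at most 50 per arm the estimate has a wide interval. Required sample size varies with the inverse square of the effect, so a moderate error in the effect becomes a large error in the sample size.

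Second, it answers a different question. A difference from waiting with usual care is not an estimate of a difference from treatment in a CFS/ME service, however precisely it is measured. In this study participants are told their group and report their own outcomes.

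What is at stake is the planning of the later trial. If the sentence is followed as written, that trial could be badly under- or over-sized.

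A smaller matter is the recruitment input. It is defined per PCT/CCG with a range, yet recruitment starts in Salford, and section 7.1 names only one adjacent CCG as an extension area.

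**Working it through.** **The plan's own figure.** Phase 2 has 100 participants, which section 7.1 derives from a recruitment funnel: 4000 invited × 0.50 responding × 0.10 screening positive × 0.50 agreeing = 100. This reproduces. It is a recruitment target, not a power calculation, and the protocol gives no figure for the definitive trial.

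**Inputs.** From the protocol: 50 per arm at most. Assumed because the protocol does not state them: outcome standardised to SD = 1, two-sided alpha 0.05, 80% power, and 40 per arm analysed as an alternative to full retention.

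**Step 1: precision of the observed effect.** SE ≈ √(2/n), with half-width 1.96 × SE.
- n = 50: √(2/50) = 0.200, half-width 0.39 SD.
- n = 40: √(2/40) = 0.224, half-width 0.44 SD.

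**Step 2: what that does to the planned size.** n per arm = 2(1.96 + 0.8416)²/d² = 15.70/d².
- Suppose the study observes 0.5 SD with 50 per arm. The 95% interval is about 0.10 to 0.90.
- d = 0.5 gives 63 per arm, d = 0.90 gives 20, and d = 0.10 gives 1570. All three effects are compatible with the same result.

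**Step 3: does imprecision alone lead to undersizing?** A plan is too small when the observed effect exceeds the true one, which happens in half of all studies. If only positive estimates lead to a trial, the share that is too small is 0.50 / P(estimate > 0).
- 40 per arm, true effect 0.3: P = Φ(0.3/0.224) = 0.91, so 0.50/0.91 = 55%.
- 40 per arm, true effect 0.5: P = Φ(0.5/0.224) = 0.987, so 51%.
- If a trial followed only when the estimate exceeded 0.2, the shares would be 74% (true effect 0.3) and 55% (true effect 0.5). The protocol states no such rule.

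**Step 4: comparator.** Take a trial sized on 0.5 SD against waiting, and suppose that the true difference against active treatment is smaller. Power = Φ(d√(n/2) − 1.96).

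| True difference (SD, assumed) | Power with 63 per arm | n per arm needed for 80% power |
|---|---|---|
| 0.5 | 80% | 63 |
| 0.4 | 61% | 99 |
| 0.3 | 39% | 175 |
| 0.2 | 20% | 393 |

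Sizing for 90% power instead gives 85 per arm, with 74%, 50% and 26% power at 0.4, 0.3 and 0.2 SD.

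**Step 5: recruitment unit.** Salford plus the one named extension area gives one or two CCGs, too few for a useful range. Section 4 does allow for wider extension into Greater Manchester. Section 7.1 plans to invite up to 32 GP practices and links participant IDs to practice, so practice-level rates will be available in any case.

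**The case against.** The best defence is that the closing sentence is not the whole plan. The same section says that published sources will be used as well, and it lists SD, attrition and recruitment as inputs, which is what a feasibility study should supply. This softens the point. It does not remove it, because none of that wording names a target difference, and the last sentence still says that the size will be determined from the estimated effects. The sentences need to be reconciled.

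A reader might infer that the resulting trial will probably be too small. The documents do not support that as a general statement. Sampling error runs both ways. The 55% in Step 3 arises only from setting aside non-positive estimates, and it falls to 51% when the true effect is 0.5 SD. The claim of a smaller effect against active care is plausible, but no figure in the protocol backs it. Usual care is unconstrained, so some controls may already receive such treatment, which would narrow the gap between the two comparators. Nor does the protocol say whether the later trial will test superiority or non-inferiority. If non-inferiority, a margin is needed, and this study's effect estimate cannot supply one.

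It is also fair to say that sizing a later trial is not among the aims in section 5 or the outcomes in section 7.5, and that the target difference can still be set when the later funding bid is written. That limits the importance of the point. Section 10 nevertheless commits to a method, and the method is easily corrected.

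**Conclusion.** The point holds for the closing sentence of section 10. Followed as written, it would base the definitive trial on an effect known only to within about ±0.39 SD (50 per arm) or ±0.44 SD (40 per arm, assumed), and on a contrast with wait-list usual care at 3 months instead of the comparator named for that trial. The resulting size would be unreliable in either direction.

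Undersizing follows only under two conditions that the protocol does not establish: a superiority design, and a smaller difference against active treatment than against waiting. Under those conditions the loss can be large, as the table shows, but its effect sizes are illustrations and not estimates.

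The conduct, data and validity of this feasibility study are unaffected. The recruitment-unit point is minor.

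**What to change.** Amend the last sentence of section 10 along these lines: *This study will supply the SD, attrition and recruitment rates for planning the definitive trial. Observed differences between arms will be reported with 95% confidence intervals and will not be used as the target difference. The target difference, or the margin if the trial tests non-inferiority, will be justified from published sources and patient input for the comparator and primary outcome of that trial.*

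This agrees with the earlier sentences of the section and leaves the choice of primary outcome open, as the protocol does now. As a minor addition, summarise recruitment per GP practice as well as per CCG, using the linkage already planned in section 7.1.

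The change is to wording only and needs no new data or participants. The cost is a little more planning work and possibly a larger definitive trial.
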